7. PHARMACODYNAMICS ANALYSES

Concentrations below the lower limit of quantitation (<LLOQ) will be treated as zero.

Concentrations above the upper limit of quantitation (>ULOQ) will use the value of ULOQ.

To measure BDNF concentrations, additional 2 blood samples will be collected at clinic visits on days 1, 4 and 7, as follows:

- pre-dose (within 60 minutes of SM administration).
- 4 hours (± 30 minutes) following SM administration.

One additional blood sample will be collected at the clinic visit on Day 10, as follows:

- 72 hours (± 60 minutes) following the last SM administration on Day 7.

The PD analysis is an exploratory analysis and will be performed using the PD population.

The change and percent change from baseline in BDNF concentrations at each time point will be analyzed descriptively. The mean (\pm SD) over time for the change and percent change from baseline will be displayed graphically. The relationship between the change and the percent changes from baseline in BDNF and the efficacy endpoints (e.g., HAM-D₆ and MADRS Total score) or plasma SPN-820 concentrations will be explored graphically using the data from the above time points. Because no PK blood samples were taken on Day 10, the BDNF data on Day 10 will not be used in the exploration of the relationship with plasma concentrations.

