8.12 Pharmacodynamic Analysis

The PD analysis is an exploratory analysis and will be performed using the PD population. The change from baseline to each time point for BDNF concentration will be analyzed descriptively.

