3.2. Definitions and Derivations

The definitions and derivations are shown in Table 2.

Table 2: Definitions and Derivations

Terminology	Definition
Baseline	Unless specified otherwise, baseline is the last non-missing assessment collected before the first dose of SM (Day 1).
Study Day	Day 1 is defined as the date of the first dose of study medication. For visits prior to Day 1, Study Day is calculated as (Event date – Day 1). For visits after Day 1, Study Day is calculated as (Event date – Day 1 + 1).
Screened Subjects	Subjects who have provided signed informed consent.

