3.3. Analysis Population

The full analysis set (FAS) includes all subjects who receive at least one dose of SM, and have a baseline and at least one post-baseline measurement of HAM-D₆.

The Safety Population includes all subjects who receive at least one dose of SM.

The Pharmacodynamics (PD) Population includes all subjects who receive at least one dose of SM and have a baseline and at least one valid post-baseline BDNF concentration.

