5.2. Secondary Efficacy Endpoints

[figure not shown]
The MADRS is a 10-item investigator-rated diagnostic questionnaire used to measure the severity of depressive episodes in subjects with mood disorders and is designed to be sensitive to changes brought on by treatment. Each question is scored from 0 to 6, the sum of the 10 subtests score will yield a total score ranging from 0 to 60. If any item score is missing, the total score will not be calculated. A total score ranging from 0 to 6 indicates that the subject is in the normal range (no depression), a score ranging from 7 to 19 indicates “mild depression”, 20 to 34 indicates “moderate depression”, and 35 to 60 indicates “severe depression”.

[figure not shown]
The CGI-S is evaluated on a 7-point scale, where 1 = Normal, not at all ill, 2 = Borderline mentally ill, 3 = Mildly Ill, 4 = Moderately ill, 5 = Markedly ill, 6 = Severely ill, and 7 = Among the most extremely ill patients.

CFB to each time point in the MADRS total score and CGI-S score will be analyzed using descriptive statistics.

Percent reduction, defined as $100 \times (\text{postbaseline} - \text{baseline}) / \text{baseline}$, in MADRS total score will be derived for each subject.

The n (%) of responders (i.e., subjects with $\geq 50\%$ reduction in MADRS total score), the n (%) of subjects in remission (i.e., subjects with MADRS total score ≤ 10) and the n (%) of subjects with a CGI-S score of 1 or 2 will be summarized at each scheduled time point.

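### BDNF values below LLOQ are set to zero, which leaves percent change undefined for a BLQ baseline and fixed at -100% for a BLQ follow-up

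*SAP*

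**What the plan says.** SAP section 7 handles the two ends of the assay range differently. At the bottom, "Concentrations below the lower limit of quantitation (<LLOQ) will be treated as zero". At the top, "Concentrations above the upper limit of quantitation (>ULOQ) will use the value of ULOQ".

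The same section then says: "The change and percent change from baseline in BDNF concentrations at each time point will be analyzed descriptively". Both measures are to be drawn as means with SDs by time point, and also plotted against efficacy endpoints and plasma concentrations.

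No visible text says what to do when the baseline is zero:

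- SAP section 3.2 defines baseline as the last non-missing value before the first dose. A BLQ result recoded to zero is non-missing, so it qualifies.
- SAP section 3.3 admits to the PD population dosed subjects who "have a baseline and at least one valid post-baseline BDNF concentration". The word valid is undefined, applies only to the post-baseline value, and does not require a quantifiable baseline.

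Protocol section 8.12 plans absolute change only: "The change from baseline to each time point for BDNF concentration will be analyzed descriptively". Percent change enters with the SAP.

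**The concern.** Percent change has the baseline in its denominator, and zero is the one substitute that makes it incalculable. The subjects affected are not a random subset. They are those with the lowest baselines, and they disappear from percent change at every time point while still counting in absolute change. The two summaries then describe different sets of subjects. At follow-up, the rule turns any value under LLOQ into a complete loss of BDNF, whatever the subject's baseline.

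The percent-change display and its plots against efficacy and plasma concentration are at stake. With no rule for a zero baseline, the programmer would have to choose one after seeing the data.

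**Working it through.** **Inputs from the documents.** BLQ set to 0 (SAP 7). Seven BDNF samples per subject, of which one is baseline and six are post-baseline (Protocol Table 1 footnote and section 6.7). About 50 subjects enrolled and about 40 completing (SAP 2.6). The assay is a validated ELISA (Protocol 9.3.4), with no LLOQ and no expected BLQ rate stated. The plan gives no figure to reproduce on this point.

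**Assumed.** Percent change = 100 × (post − baseline)/baseline. The SAP writes this form for MADRS (section 5.2) but gives no formula for BDNF. Values below are in units of LLOQ.

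**1. BLQ baseline.** 100 × (post − 0)/0 is undefined for any follow-up value, and is 0/0 if the follow-up is also BLQ. The subject is lost from percent change at all 7 − 1 = 6 post-baseline time points.

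**2. Quantifiable baseline b, BLQ follow-up.** 100 × (0 − b)/b = -100% for every b. The true change can lie anywhere from -100% up to 100 × (1 − b)/b:

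| Baseline (× LLOQ) | Zero rule | Smallest true fall possible | With LLOQ/2 |
|---|---|---|---|
| 1.05 | -100% | -4.8% | -52.4% |
| 1.5 | -100% | -33.3% | -66.7% |
| 2 | -100% | -50.0% | -75.0% |
| 5 | -100% | -80.0% | -90.0% |

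**3. How often a baseline is undefined.** Chance of at least one BLQ baseline = 1 − (1 − p)^n, for assumed p:

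| p | n = 40 | n = 50 | Expected number, n = 50 |
|---|---|---|---|
| 2% | 55% | 64% | 1.0 |
| 5% | 87% | 92% | 2.5 |
| 10% | 99% | 99% | 5.0 |

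**4. Effect on the summaries.** Simulated lognormal BDNF with no true change, log SD 0.6 between and 0.4 within subjects (both assumed), 2 million subjects, LLOQ placed to give each BLQ rate:

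| Percent change | Full data | 2% BLQ | 5% BLQ | 10% BLQ |
|---|---|---|---|---|
| Median, zero rule | 0 | -1.0 | -2.3 | -4.1 |
| Median, LLOQ/2 | 0 | 0 | 0 | 0 |
| Mean, zero rule | 17.3 | 15.0 | 12.3 | 8.4 |
| Mean, LLOQ/2 | 17.3 | 18.9 | 20.4 | 22.1 |
| SD, zero rule | 72.0 | 71.0 | 70.4 | 70.0 |
| SD, LLOQ/2 | 72.0 | 78.5 | 83.4 | 88.0 |

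The full-data mean of about 17% is not a treatment effect. It arises from averaging ratios to a noisy baseline: exp(0.4²) − 1 = exp(0.16) − 1 = 17.4%. With LLOQ/2 the geometric mean ratio is 1.00 at all three rates, which is the correct answer for no change.

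**5. The SD can go either way.** In the table it falls under the zero rule, because dropping low baselines removes large percentage rises. With a within-subject log SD of 0.28 it rises, from 45.1 to 47.7 at 10% BLQ. In the simplest case, one BLQ follow-up among 40 otherwise unchanged subjects gives a mean of -100/40 = -2.5 and an SD of 15.8.

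**The case against.** The frequency is unknown. A validated assay may return no BLQ values at all, in which case nothing changes. The endpoint is exploratory, the analysis is descriptive and there are no hypotheses (SAP 3.6). The protocol's endpoint, absolute change, stays defined for every subject with both values. In the simulation its mean is essentially unaffected, and its SD moves by at most 2% (0.916 to 0.934). SAP 3.1 already lists the median, quartiles and n for continuous variables, so a reader could see that subjects had dropped out. All of this stands and limits the severity. It does not supply the missing rule for a zero baseline, and it does not make -100% a sensible value for a result just under LLOQ.

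Four stronger readings are tempting, and none is supported:

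- *The zero rule biases the mean downward.* It lowers the mean relative to full data, but that 17% is itself an artefact when the true change is zero. In this model the zero rule moves the mean towards the truth. The median shift is the clear distortion, and it is small.
- *The zero rule inflates the SD.* The direction depends on the assumed within-subject variation.
- *Subjects vanish from the exploratory plots.* They vanish only from the percent-change versions. SAP 7 also plots absolute change.
- *LLOQ/2 is enough by itself.* With the planned arithmetic mean and SD it makes both worse than the zero rule does.

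**Conclusion.** The point holds in a limited form. Given the standard percent-change formula, the undefined values and the forced -100% follow from the SAP's own rules by algebra and need no assumption about rates. How much they matter in practice cannot be judged from the documents. The probabilities and the median shifts of about -1, -2 and -4 points rest on assumed BLQ rates of 2%, 5% and 10%, and the shifts also rest on the assumed log SDs.

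Zero is also out of line with the SAP's other conventions. BDNF above ULOQ takes the limit, and a laboratory value reported as less than x takes x (SAP 8.2). Parts of the SAP are removed or blacked out, so a rule elsewhere cannot be fully excluded, but none is visible in section 7, which governs BDNF. Severity: nice to have.

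**What to change.** In SAP section 7:

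- For relative change, replace zero with a stated positive substitute such as LLOQ/2.
- Summarise and plot relative change as the geometric mean ratio to baseline, or as the median with quartiles, in place of the arithmetic mean (SD) percent change. This must accompany the substitute: LLOQ/2 should not be combined with the arithmetic mean and SD.
- Report the number of BLQ values at baseline and at each time point.

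The cost is one or two SAP sentences and minor programming, with no change to trial procedures. The downside is that LLOQ/2 is an arbitrary value, and the size of an individual ratio from a BLQ baseline depends on it. The BLQ counts let a reader judge how far that matters.

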8. SAFETY

The assessment of overall safety and tolerability will be based on adverse events, laboratory values, vital signs and weight, ECGs, physical examinations, C-SSRS, CADSS, and BPRS+ using the safety population.

8.1. Adverse Events

All adverse events (AEs) will be coded using the MedDRA v26.1. The MedDRA version used for reporting will be specified in the footnote of the applicable output.

A treatment-emergent adverse event (TEAE) is defined as an AE with a start date on or after the date of the first dose of study medication, or that worsened in severity following the first dose of study medication. Any event that is present at baseline but worsens in severity will be determined by the Investigator and entered in the CRF as new AE. Thus, all eCRF-collected AEs that occurred on or after the date of the first dose of study medication are TEAEs.

Based on the Investigator's determination, the severity of TEAEs will be classified as mild, moderate or severe. For summaries by severity, a subject experiencing multiple AEs in the same preferred term with different intensities will only be counted once with the maximum severity. If severity is missing, then the maximum severity will be assumed for the analysis (i.e., severity = severe).

The relationship between the study medication and a TEAE is determined by the Investigator and will be classified as unrelated (i.e., unlikely related and not related) or related (possibly related and definitely related). TEAEs with missing relatedness will be counted as definitely related. For summaries by relationship, a subject experiencing multiple AEs in the same preferred term with different relationship will only be counted once with the most related occurrence.

An overview of TEAE will include summaries of number and percent of subjects who had at least one TEAE, Treatment-emergent serious AE (SAE), Treatment-emergent SAEs related to SM, TEAE leading to death, TEAE by maximum severity, TEAE by relationship, and TEAE leading to withdrawal of study medication.

In addition to the overview of TEAE summary, the following TEAEs summary tables will be provided:

- Treatment-Emergent Adverse Events by System Organ Class and Preferred Term
- Most Common ($\geq 5\%$) Treatment-Emergent Adverse Events by Preferred Term
- Treatment-Emergent Adverse Events by System Organ Class, Preferred Term, and Severity
- Treatment-Emergent Adverse Events by System Organ Class, Preferred Term, and Relationship to Study Medication
- Treatment-Emergent Serious Adverse Events by System Organ Class and Preferred Term
- Treatment-Emergent Adverse Events Leading to Withdrawal of Study Medication by System Organ Class and Preferred Term

- A data listing of death will be provided. If no death occurred, a blank listing with “No subject died on this study.” will be presented.

A subject with multiple occurrences of an AE will be counted only once in the AE category per SOC and PT for summary tables. The sorting will be based on the decreasing frequency.

Listing will be provided for all AEs, SAE, and TEAE Leading to Withdrawal of Study Medication.

8.2. Laboratory

Laboratory data will be collected according to the schedule in Section 11.1. Different local laboratories may have different normal (reference) ranges and units for each of the laboratory tests (parameters). Thus, all numerical laboratory values will be converted to the International System of Units (SI) and then normalized to a standard set of reference ranges as described by Chuang-Stein (1992 and 2001). The normalization process will be performed separately by each of the laboratory parameters as described in Section 11.2. These normalized data will be used for summary statistics. All data summaries and listings will be provided in SI.

Numerical laboratory values reported in a special form (e.g., $< x$, $\leq x$, $> x$, or $\geq x$) will be derived as a numerical value, x , for summary statistics. However, the originally reported values in the special form (i.e., $< x$, $\leq x$, $> x$, or $\geq x$) will be presented in data listings.

8.2.1. Absolute Value and Change from Baseline

Absolute values and CFB in haematology, serum chemistry and urinalysis variables will be summarized descriptively by visit.

For visit-based summary tables, in the event of repeat assessments within visit window, the first non-missing value will be used in the tabulations. Results from unscheduled visits will not be used in summary statistics but will be included in data listings.

8.2.2. Shift in Laboratory Values

Compared to the original reference range, each laboratory test value will be classified as low, normal, high or missing. Shift tables of laboratory data from baseline will be summarized using number and percentage of subjects by visit.

The shift from baseline to the worst post-baseline laboratory values will also be presented. The worst post-baseline value is defined as the highest or the lowest value (for some parameters may be applicable in both directions) among all post-baseline values collected at any time from all (scheduled and unscheduled) visits.

8.2.3. Clinically Notable Values of Laboratory

Values of laboratory tests are considered clinically notable values (CNV) if they meet the selected criteria in Section 11.3. The number and percentage of subjects with post-baseline CNV will be summarized by overall. For each individual laboratory parameter, the denominator of the percentage includes all subjects who have a non-CNV (or including missing) at baseline and at least one post-baseline assessment (including unscheduled visit) for that parameter. And the numerator of the percentage is the number of subjects who are included in the denominator and

have a CNV at post-baseline for that parameter. A supportive listing of subjects with any CNVs will be provided.

Number and percent of subjects who meet Hy's Law criteria (ALT or AST $>3 \times$ ULN, along with total bilirubin $>2 \times$ ULN and a non-elevated ALP $<2 \times$ ULN, where ULN denotes the upper limit of the normal range) will be summarized.

All laboratory data including repeated values and results from unscheduled visits will be provided in data listings with indication of higher or lower than the reference range of each laboratory test.

8.3. Vital Signs

8.3.1. Absolute Value and Change from Baseline

The CFB in vital sign variables will be calculated for each post-baseline visit. The postural change in blood pressure and pulse rate from sitting to standing will be calculated for each visit. The analyses of vital signs will be summarized descriptively in the same manner as described in Section 8.2.1.

8.3.2. Shift in Vital Signs

The shift analyses of vital signs will be performed in the same manner as described in Section 8.2.2. Vital sign normal ranges are presented in Section 11.4.

8.3.3. Clinically Notable Values of Vital Signs

The number and percentage of subjects meeting the criteria of clinically notable values specified in Section 11.5 will be summarized by overall. For each individual vital sign parameter, the denominator of the percentage includes all subjects who had a baseline and at least one post-baseline assessment (including unscheduled visit) for that parameter. And the numerator of the percentage is the number of subjects who are included in the denominator and have a CNV at post-baseline for that parameter.

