2.4 Clinical Studies

[figure not shown]
The PK, pharmacodynamics (PD), preliminary efficacy, and safety of SPN-820 have been evaluated in 6 completed Phase 1 clinical studies.

Completed Studies

A total of 145 adult subjects have been exposed to SPN-820 in the Phase 1 studies, including 129 healthy subjects and 16 subjects with TRD. Single doses up to 2400 mg and multiple doses up to 3000 mg for 7 days have been administered in the Phase 1 clinical studies.

- Study NAV-17A-001 was a Phase 1a/1b, randomized, two-part, double-blind, placebo-controlled, on-site study of single ascending dosage levels of SPN-820 or placebo in 48 healthy subjects (Part A) and a single dose of SPN-820 2400 mg or placebo in 32 subjects with TRD (Part B).
- Study NAV-17A-002 was a Phase 1, randomized, double-blind, placebo-controlled, on-site, single-dose study to evaluate the safety, PK, metabolomic and proteomic profiles of SPN-820 in plasma and cerebrospinal fluid (CSF) in healthy male subjects between the ages of 18 and 55 years.
- Study NAV-17A-003 was a randomized, double-blind, placebo-controlled, on-site study of the effects on quantitative electroencephalography and event-related potential of 2 sequential doses of SPN-820 or placebo administered 48 hours apart, to healthy adult male subjects.
- Study NAV-17A-004 was a Phase 1, randomized, double-blind, placebo-controlled, single-center study of the safety, tolerability, and PK of multiple ascending doses of SPN-820 in healthy subjects.
- Study NAV-17A-005 was a Phase 1, 4-period, 4-treatment, 4-sequence crossover study in which subjects received a single dose of SPN-820 400 mg oral solution, 400 mg capsule, 1600 mg oral solution, and 1600 mg capsule under fasted conditions.
- Study NAV-17A-006 was a Phase 1, open-label, single-dose, mass balance study to assess the disposition of [14C]-SPN-820 in healthy male subjects.

Completed Study Results

[figure not shown]

Safety

The majority of treatment-emergent adverse events (TEAEs) reported by healthy subjects were reported as mild, none were severe, and all resolved. The most frequently reported TEAEs by healthy subjects included dizziness (postural dizziness and orthostatic hypotension) nausea, headache, and somnolence. Two subjects who received single doses of SPN-820 400 mg discontinued due to adverse events (AEs): muscle strain, nausea, and vomiting (n=1); vomiting (n=1).

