11.5. Criteria for Clinically Notable Vital Sign Values

Table 7: Clinically Notable Vital Sign Values

Parameter	Criteria
Sitting Systolic Blood Pressure	≤ 90 and/or ≥ 180 mmHg Change from baseline of ≥ 20
Sitting Diastolic Blood Pressure	≤ 50 and/or ≥ 105 mmHg Change from baseline of ≥ 15
Sitting Heart Rate	≤ 50 and/or ≥ 120 bpm Change from baseline ≥ 30
Standing Systolic Blood Pressure	≤ 90 and/or ≥ 180 mmHg Change from baseline of ≥ 20
Standing Diastolic Blood Pressure	≤ 50 and/or ≥ 105 mmHg Change from baseline of ≥ 15
Standing Heart Rate	≤ 50 and/or ≥ 120 bpm Change from baseline ≥ 30
Change from sitting to standing at same Assessment in SBP	≥ 20 mm Hg
Change from sitting to standing at same Assessment in DBP	≥ 10 mm Hg

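### SAP 8.3.3 does not separate vital-sign notable values present before the first dose from those that first appear afterwards; the gap matters most for the sitting-to-standing criteria

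*SAP*

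**What the plan says.** **Vital signs (SAP 8.3.3).** For each parameter, "the denominator of the percentage includes all subjects who had a baseline and at least one post-baseline assessment (including unscheduled visit) for that parameter". The numerator is the number of "subjects who are included in the denominator and have a CNV at post-baseline for that parameter". A baseline value is required, but baseline status is not used.

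**Laboratory values (SAP 8.2.3).** Here "the denominator of the percentage includes all subjects who have a non-CNV (or including missing) at baseline and at least one post-baseline assessment". The numerator is drawn from that restricted group, and a supportive listing of subjects with any CNV is promised. SAP 8.3.3 promises no such listing.

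**Criteria (SAP 11.5, Table 7).** The row for sitting systolic pressure reads "≤ 90 and/or ≥ 180 mmHg Change from baseline of ≥ 20" and the row for sitting heart rate reads "≤ 50 and/or ≥ 120 bpm Change from baseline ≥ 30". Diastolic pressure has the same two-line layout, with limits of 50 and 105 mmHg and a change of 15. Nothing says whether the two lines are alternatives or must both be met. The postural rows, such as "Change from sitting to standing at same Assessment in SBP", give a single threshold (20 mmHg systolic, 10 mmHg diastolic), no direction and no reference to baseline.

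**Related output.** SAP 8.3.1 calculates the postural change at each visit. SAP 8.3.2 gives shift tables against the Table 6 ranges, which have no entry for postural change. SAP 8.5.3 counts ECG criteria on any post-baseline value, without a baseline exclusion.

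**The concern.** One SAP uses one term, CNV, for two different percentages and gives no reason. The laboratory figure is new occurrence. The vital-sign figure is new occurrence plus recurrence of what was already there.

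There is no control group, so each subject's own baseline is the only reference for background. Orthostatic blood pressure and pulse are named safety measures. Protocol 2.4 lists postural dizziness and orthostatic hypotension among the most frequent events in healthy subjects given the drug. Eligibility does not clear these findings out beforehand: Protocol 4.2.3 excludes orthostatic hypotension only when it is symptomatic and clinically significant, and otherwise leaves vital signs to the investigator's judgment with no numeric limit. Subjects with symptom-free postural changes at baseline can therefore be enrolled and counted again after dosing. A reader of the table could not tell how many of the flagged subjects were in that position.

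**Working it through.** The documents state no CNV rate, so there is no figure of the plan's own to reproduce. The check compares the two rules and then sizes the difference on stated assumptions.

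**1. The rules as proportions.** Let N be the subjects with a baseline and a post-baseline value, k those meeting the criterion at baseline, q the share of those k who meet it again afterwards, and p the new-onset rate among the other N − k.

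- Vital-sign rule (8.3.3): (kq + (N − k)p) / N
- Laboratory rule (8.2.3): p, among N − k subjects
- Difference: k(q − p) / N

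The vital-sign rate is higher whenever baseline-positive subjects show the value more often afterwards than other subjects do. The documents do not give k, q or p.

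**2. A small count, for illustration.** Take N = 50, with 3 positive at baseline, 2 of them recurring and 1 new case. The vital-sign rule gives 3/50 = 6.0%; the laboratory rule gives 1/47 = 2.1%.

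**3. A modelled postural criterion with no drug effect.** The assumptions, none of them from the documents, are:

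- standing-minus-sitting diastolic change with mean +3 and SD 8 mmHg, rounded to integers;
- within-subject correlation 0.5 or 0.7;
- the criterion read as a fall of at least 10 mmHg.

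The three post-baseline visits (days 4, 7 and 10) come from the schedule of events. Share positive at baseline: Φ((−9.5 − 3)/8) = Φ(−1.56) = 5.9%, or about 3 of 50. Simulating 400,000 subjects gives:

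| Correlation | Flagged under 8.3.3 | Of which positive at baseline | Flagged under the 8.2.3 rule |
|---|---|---|---|
| 0.5 | 13.7% | 3.0 points (22% of those flagged) | (13.7 − 3.0)/(100 − 5.9) = 11.4% |
| 0.7 | 11.9% | 3.9 points (33% of those flagged) | (11.9 − 3.9)/(100 − 5.9) = 8.5% |

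In 50 subjects the pre-existing cases number 0.030 × 50 = 1.5 to 0.039 × 50 = 1.95. The rate falls by 13.7 − 11.4 = 2.3 to 11.9 − 8.5 = 3.4 points, or 1.2 to 1.7 subjects in 50.

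**4. Which Table 7 rows are exposed.**

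- *Postural rows:* exposed on any reading. They have no baseline term, and without a Table 6 range they have no shift table.
- *Absolute limits, lines read as alternatives:* exposed. For heart rate of 50 or below (assumed mean 70, SD 11), 8.0-9.2% are flagged, with 1.7-2.3 points pre-existing. For systolic pressure of 90 or below (assumed mean 116-122, SD 13), 0.2-1.4 points are pre-existing, which is under 1 subject in 50.
- *Absolute limits, both lines required:* essentially not exposed. A subject already at the limit counts only after a further change from baseline; in the heart-rate model the pre-existing share was 0.0%.
- *Change-from-baseline lines on their own:* not exposed, since they cannot be met at baseline.

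**5. What the shift tables recover.** The lower limits for systolic pressure and heart rate are the same in Tables 6 and 7 (90 and 50). The shift tables therefore show who was low before dosing, except at exactly the limit. For diastolic pressure the lower limits differ (60 against 50), so the match is only partial.

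**The case against.** The strongest reply is that SAP 8.3.3 does what it says. It reports subjects with a post-baseline CNV and never calls them new or treatment-emergent. An any-post-baseline count is a legitimate descriptive choice, and the ECG incidence in SAP 8.5.3 follows the same convention. That stands: nothing is mislabelled, and vital signs are not the only exception to the laboratory rule. What remains is that the table does not show how many flagged subjects were already positive.

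A reader might infer that this percentage is the main vital-sign result. The documents do not support that. Protocol 8.13 asks for actual values, change and shift from baseline and does not ask for CNV rates. The SAP also supplies the postural change by visit, and individual data are listed, so baseline status could be traced by hand.

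A reader might also infer that low pressure and slow pulse are affected to the same degree. That depends on an unstated reading of Table 7, and the shift tables already cover most of it for systolic pressure and heart rate.

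Two further points stand. Most of the modelled rate survives the laboratory rule (11.4/13.7 = 83% and 8.5/11.9 = 71%), so that rule does not replace a control group. And copying it would hide worsening: a subject whose postural change went from 20 to 45 mmHg would leave both numerator and denominator.

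**Conclusion.** The inconsistency between SAP 8.2.3 and 8.3.3 is plain in the text. It matters most for the postural criteria, where no shift table separates prior from new findings. For the absolute limits it holds only if Table 7's two lines are alternatives, and even then the shift tables show most of the baseline status for systolic pressure and heart rate.

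The size is modest: 1 to 2 subjects in 50 on the diastolic postural criterion. That rests on an assumed distribution, on the assumed correlations and on reading the criterion as a fall. That a recurring baseline-positive subject is counted does not rest on those assumptions. This is one descriptive safety table and efficacy is untouched, but the correction is cheap and worth making before the tables are produced.

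**What to change.** In SAP 8.3.3 and Table 7:

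- For each absolute and each postural criterion, report n/N with a post-baseline CNV separately for subjects who did not meet it at baseline and for those who did. This shows new occurrence and keeps every subject in view.
- Keep the full denominator for the change-from-baseline criteria.
- State whether the absolute and change lines in a row are alternatives or must both be met.
- State the direction of the postural criterion; as written, a rise on standing would also qualify.
- Add a supportive listing of subjects with vital-sign CNVs, as 8.2.3 does for laboratory values.

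The cost is some SAP wording, extra table columns and one listing, with no new data. The new-occurrence rates will be slightly lower than the rates as now defined, and the baseline-positive group will be small, so its counts should be read as counts.
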